Participants: 70 overweight and obese healthy male and female volunteers aged between 18 and 65 years with body mass index (BMI) of 25-35 kg/m².

Support of number of volunteers: Based on previous work we anticipate that a hypo-caloric diet alone will cause a weight loss of 3.0 ± 2.5 kg, whilst the addition of propionate-ester will cause a weight loss of 5.0 ± 2.5 kg. A power calculation shows that 26 volunteers will be need per group to detect a significant difference between groups ($p=0.05$, 0.80 power). 70 volunteers will be recruited to allow a 25% drop-out rate.

Visit 1: Health Screening

Participants will attend the NIHR/Wellcome Trust Imperial Clinical Research Facility at Hammersmith Hospital where their eligibility will be assessed. They will have a blood test (FBC, ALT, HbA1C, renal function, and lipids) and height and weight measurements will also be taken. They will also have an electrocardiogram (ECG) and blood pressure will be recorded. All women of childbearing age will have a pregnancy test.

Participants will be told not to start any other new diets or intensive exercise regimes during the study period as this may give us conflicting results.

Visit 2: Acclimatization visit (Week 0)

The main objective of this visit is to fully acclimatize the participants to the study before the baseline visit.

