The day prior to the study visit, participants will be requested to refrain from strenuous exercise and alcohol. Participants will then be requested to fast overnight (they are allowed to drink water) and will come to the NIHR/Wellcome Trust Imperial Clinical Research Facility at Hammersmith Hospital the following morning. Fasting saline flushes will be done through an intravenous peripheral cannula at -10 and 0 min. Resting energy expenditure will be measured with a standard indirect calorimeter. The calorimeter captures expired air from a large, transparent canopy, worn over the head and thorax, and is typically very well tolerated. Each participant will be asked to lie in a semi-recumbent position under the canopy. Once the carbon dioxide content of the air entering the chamber has stabilised, measurements will be taken for 20 min in order to assess the participants' resting metabolic rate (RMR) and respiratory quotient (RQ). The calories needed per day for each subject will be estimated and a -500 kcal/day diet will be provided to the participants to follow for the rest study period. Participants will be asked to complete a 7days-food diary in order to form a suitable individualised diet. A weight management booklet will be designed to each participant, where their resting energy requirement will be estimated and a healthy diet plan will be designed. This will also include a supplementary material of the portions required and list of different substitutes to be taken per food group. The same booklet content was previously designed and used in a trial that was ethically approved with a reference number of 12/LO/0139 version 2: 31/07/2012.

Participants will then receive a standardised breakfast (0 min). Postprandial saline flushes will be given at 15, 30, 60, 90, 120, 180, and 240 min.

Appetite and satiety will be assessed by visual analogue scale every 60 min and breath hydrogen concentration will be measured at the same time, as a marker of colonic fermentation. Food intake will be assessed at 240 min by offering a free buffet meal served in excess.

Visit 3: Study visit 1 (Week 1)

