The same measurements collected during the acclimatization visit will be repeated. The only difference would be in collecting 10 ml of postprandial blood, instead of flushing saline, at each time point of 15, 30, 60, 90, 120, 180, and 240 min to measure hormones and metabolites. These will include glucose, insulin, gastrointestinal and appetite hormones (GLP-1, pro-glucagon-derived peptide, PYY, PP, Ghrelin, Cholecystokinin), and short chain fatty acids level

Participants will be randomised to take 10 g of Propionate ester or Inulin (control) dietary supplement once a day for 84 days (12 weeks). Supplements will be given to participants in ready-to-use sachets and instructed to mix the contents into their -500 kcal/day individual diet. An independent researcher (i.e. not linked to the study) will be given the task of randomisation, which will be by sealed envelopes.

Urine will be collected throughout the study visit to measure propionate and urea concentrations. Subjects will empty their bladder before the test breakfast and collect all urine thereafter for a period of 240 min. Subjects will be provided with an appropriate measurement container to collect urine and will be asked to note the total volume following each collection.

Subjects will be asked to collect a stool sample to assess propionate levels. Subjects will collect a sample of the first stool they pass after 10:00 pm on the study day. Participants will be provided with detailed instructions of how to do this and will be given appropriate containers.

Visits 4 and 5: Study visits 2, 3 (Week 4 and week 8):

Will involve short visits to monitor weight and dietary compliance to the diet, through collecting 7-days food intake diary and taking anthropometry measurements.

Visit 6: Study visit 4 (Week 12):

At the end of 84 day supplementation period, participants will attend the NIHR/Wellcome Trust Imperial Clinical Research Facility at Hammersmith Hospital to and all measurements collected during Study Visit 1 will be repeated.

PARTICIPANT ENTRY**INCLUSION CRITERIA**

- Healthy overweight and obese volunteers (body mass index (BMI) of 25-35 kg/m²)
- Age between 18-65 years (inclusive)
- Having blood results for the following tests in the ranges of:
 - HbA1C 20-41 mmol/mol haemoglobin
 - ALT 0-40 IU/L
 - FBC :

| TEST | MALE | FEMALE |
|---------------------------------|-------------|-------------|
| WBC (x10 ⁹ /L) | 4.2-10.6 | 4.2-11.2 |
| RBC (x10 ¹² /L) | 4.23- 5.46 | 3.73-4.96 |

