Statistical analysis perform with IBM SPSS version 23. Graphs prepare with GraphPad Prism version 7.04. Data will be checked for normality using a Shapiro-Wilk test (defined as $P \geq 0.01$). Percentage of weight loss will be calculated using the weight at the end of the intervention divided by the baseline weight multiplied by 100. The results express as mean difference with \pm SEM. Mean of data will be compared within and between groups using a paired t-test or Wilcoxon signed-rank test where applicable. Analysis of variance will assess the impact of two different interventions (IPE and Inulin) on participant blood parameters across the 12-week supplementation period (baseline and week 12), with the supplementation group used to determine between-subjects differences. A p-value ≤ 0.05 will consider significant.

References:

- Abete, I. et al., 2008. Effects of two energy-restricted diets differing in the carbohydrate/protein ratio on weight loss and oxidative changes of obese men. *International journal of food sciences and nutrition*, 60 Suppl 3(783016891), pp.1–13. Available at: <http://www.ncbi.nlm.nih.gov/pubmed/18654910>.
- Bouché, C. et al., 2002. Five-week, low-glycemic index diet decreases total fat mass and improves plasma lipid profile in moderately overweight nondiabetic men. *Diabetes Care*, 25(5), pp.822–828.
- Brown, A.J. et al., 2003. The orphan G protein-coupled receptors GPR41 and GPR43 are activated by propionate and other short chain carboxylic acids. *Journal of Biological Chemistry*, 278(13), pp.11312–11319.
- Chambers, E.S. et al., 2015. A novel dietary strategy to increase colonic propionate production in humans and improve appetite regulation and bodyweight management. *Nutrition Bulletin*, 40(3), pp.227–230. Available at: <http://doi.wiley.com/10.1111/nbu.12157>.
- Chambers, E.S. et al., 2014. Effects of targeted delivery of propionate to the human colon on appetite regulation, body weight maintenance and adiposity in overweight adults. *Gut*, 64(11), pp.1744–1754. Available at: <http://www.ncbi.nlm.nih.gov/pubmed/25500202>.
- Cleave, T.L., 1974. The Saccharine Disease - Chapter 5. In Bristol. Available at: http://journeytoforever.org/farm_library/Cleave/cleave_ch5.html [Accessed February 28, 2016].
- Cordain, L. et al., 2005. Origins and evolution of the Western diet : health implications for the. *The American Journal of Clinical Nutrition*, 81, pp.341–354.

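### Sex enters neither the described allocation nor the between-arm analysis of weight, so a small, conditional gain in precision is forgone

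*Combined protocol and SAP*

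**What the plan says.** Section 2 of the protocol (Participants) plans to enrol "70 overweight and obese healthy male and female volunteers aged between 18 and 65 years", with BMI 25-35. The sample size paragraph expects that "a hypo-caloric diet alone will cause a weight loss of 3.0 ± 2.5 kg", and that "the addition of propionate-ester will cause a weight loss of 5.0 ± 2.5 kg". From this it concludes that "26 volunteers will be need per group to detect a significant difference between groups", and adds that "70 volunteers will be recruited to allow a 25% drop-out rate".

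The allocation method is stated once, under Visit 3: a researcher outside the study "will be given the task of randomisation, which will be by sealed envelopes". How the sequence is generated, and whether it is blocked, stratified or minimised, is not described.

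The Statistical Plan compares group means by t-test or a Wilcoxon test. Its analysis of variance for blood parameters has supplementation group as the only between-subjects factor. Neither sex nor baseline weight is named as a covariate. Sex is known at screening, because several blood-count limits and the creatinine limits in the inclusion criteria differ for men and women.

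**The concern.** The outcome that sets the sample size is absolute weight lost, in a mixed-sex group with a fairly wide range of body size. If men and women lose different amounts on this diet, two things follow when sex is ignored. The arms can differ by chance in their share of women, which moves the estimated treatment difference in that particular trial. The between-sex variance also stays in the error term.

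With about 52 completers, chance imbalances of some size are not rare. Sex is already recorded and an independent person already handles the envelopes, so using sex would cost almost nothing. At stake is the precision of a 2 kg contrast whose planned power is barely above its 80% target.

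**Working it through.** **Inputs from the documents.** Difference 5.0 − 3.0 = 2.0 kg. SD 2.5 kg (the ± is unlabelled; read as an SD it reproduces the stated size). Power 0.80. Significance rule: "A p-value ≤ 0.05 will consider significant". 26 per group. 70 recruited with 25% drop-out.

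**Assumptions.** Two-sided test, 1:1 allocation, equal drop-out by arm, an independent two-sample t-test for weight loss, share of women f = 0.5 among completers, and a sex gap g in mean weight loss of 0.5 to 2 kg. The documents give neither f nor g.

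**Step 1: the plan's own figure.** SE = 2.5 × √(2/26) = 0.693 kg. Noncentrality = 2.0/0.693 = 2.88 on 50 degrees of freedom. Power is 80.7% at 26 per group and 79.1% at 25, so 26 is reproduced. Recruitment: 52/0.75 = 69.3, rounded up to 70.

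**Step 2: chance imbalance without stratification.** The SD of the between-arm difference in share of women is √(2 × 0.25/26) = 0.139. The probability of a gap of 20 percentage points or more is 0.13 if each arm's count of women is binomial, or 0.17 if exactly 26 of the 52 completers are women. A 20-point gap moves the contrast by 0.2 × g: 0.1 kg at g = 0.5 and 0.4 kg at g = 2. The SD of the chance shift is 0.139 × g, which is 0.14 kg at g = 1 and 0.28 kg at g = 2.

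**Step 3: is that shift additional to the planned error?** No, provided the 2.5 kg SD comes from a mixed-sex group. The planned variance is 0.693² = 0.481. At g = 1 it splits into 0.139² + 0.679² = 0.019 + 0.461; at g = 2 into 0.277² + 0.635² = 0.077 + 0.404. Both sum to 0.481. The shift is a part of the 0.693 kg standard error that could be removed.

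**Step 4: what using sex would gain.** Variance share R² = g² × f(1 − f)/2.5². Residual SD = 2.5 × √(1 − R²). With full balance and adjustment, SE = residual SD × √(2/26) on 49 degrees of freedom. With adjustment alone, the variance is divided by (1 − d²), where d is the chance difference in share of women, and power is averaged over the hypergeometric distribution of d.

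| Assumed g (kg) | R² | Residual SD | SE, balanced and adjusted | Power, unadjusted | Power, adjusted only | Power, stratified and adjusted |
|---|---|---|---|---|---|---|
| 0.5 | 0.01 | 2.487 | 0.690 | 80.7% | 80.3% | 81.1% |
| 1.0 | 0.04 | 2.449 | 0.679 | 80.7% | 81.5% | 82.3% |
| 1.5 | 0.09 | 2.385 | 0.661 | 80.7% | 83.5% | 84.2% |
| 2.0 | 0.16 | 2.291 | 0.635 | 80.7% | 86.3% | 87.0% |

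Stratifying adds 0.7 to 0.8 of a point in every row. At 1.5 and 2 kg most of the gain comes from adjustment. At 1 kg the two contribute about equally, to a total of 1.6 points. At 0.5 kg adjustment alone loses 0.4 of a point. With 70% women the gains are slightly smaller: about 82% at 1 kg and 86% at 2 kg, stratified and adjusted.

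**Step 5: validity, by simulation (10,000 trials per setting, g = 1 and 2).** Unstratified and unadjusted: type I error 0.052 and 0.047, power 0.81 at both. Stratified but unadjusted: type I error 0.045 and 0.034, power 0.81 and 0.83. Stratifying without adjusting therefore makes the test conservative and recovers little.

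**Step 6: drop-out.** Stratification balances about 35 randomised per arm, not the 26 who finish. If completers are a random 26 of 35, the SD of the difference in share of women is still 0.139 × √(9/34) = 0.071, about half the unstratified value. The last column of the table is therefore an upper limit.

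**The case against.** The case for leaving the plan alone is substantial.

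- The sex gap is not in the documents. The protocol says that "a -500 kcal/day diet will be provided to the participants", set from individually estimated needs, so the planned deficit in kcal is the same for men and women and may narrow any gap in kilograms. A 2 kg gap would equal the whole anticipated treatment effect. This stands: the benefit is conditional, and at 0.5 kg it is negligible.
- The Statistical Plan also expresses weight as a percentage of baseline, which removes part of any gap driven by body size. This stands too, although the trial is sized on kilograms.
- Unstratified randomisation is a legitimate choice in a small trial, and stratifying adds under one power point. This also stands.

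Three stronger readings are tempting. A reader might infer that allocation will be unstratified. The text does not say so; it is silent on blocks and strata. A reader might infer that the treatment estimate will be biased. It will not be in expectation, because allocation is random; only the estimate in a single trial moves, and the standard error already allows for that. A reader might infer that the trial is underpowered. The stated inputs give 80.7% against a target of 80%, and if the 2.5 kg SD comes from a mixed-sex group the sex-related variance is already in it. The plan attributes its figures only to previous work, so that condition cannot be checked.

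What survives is that the described analysis ignores a recorded baseline factor that may predict the outcome and could be used almost free of charge.

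**Conclusion.** The point holds as a minor matter of efficiency. The documents describe no blocking or stratification and no use of sex in the comparison of weight. If sex predicts kilograms lost, some precision is forgone: the power gain is up to about 0.4, 1.6, 3.5 or 6.2 points for an assumed gap of 0.5, 1, 1.5 or 2 kg. Where the gain is worth having (1.5 kg or more), most of it comes from adjusting the analysis.

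The figures assume half the completers are women, 26 per arm, a two-sided test and an SD of 2.5 kg from a mixed-sex group. They also assume an unpaired between-arm t-test. The Statistical Plan names a paired t-test or signed-rank test for comparisons both within and between groups; that is a separate matter, and the sample size matches the unpaired reading. The planned 26 per group need not change.

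**What to change.** 1. In the Statistical Plan, include sex as a factor in the between-arm analysis of weight change, specified before the data are seen. This carries most of any worthwhile gain.
2. Under Visit 3, state that the independent researcher prepares two numbered envelope series, one for men and one for women, allocated 1:1 in permuted blocks of randomly varying size. Blocking also keeps the arm sizes close, which the present text does not address. If this step is taken, step 1 should go with it, since stratifying without adjusting makes the test conservative.

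The cost is one protocol sentence and one model term, with no extra participants, visits or measurements. The downsides are one lost degree of freedom, no real gain if the sex gap is small (at 0.5 kg, adjustment without stratification would cost about 0.4 of a power point), and slight predictability near the end of a block, which varying the block size limits.

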| Hb(g/L) | 130-168 | 114-150 |
| PCV (Ratio) | 0.390-0.500 | 0.350-0.450 |
| MCV (fl) | 83.5-99.5 | 83.5-99.5 |
| MCH (pg) | 27.5-33.1 | 27.5-33.1 |
| MCHC (g/L) | 315-350 | 315-350 |
| RDW | 10.0-16.0 | 10.0-15.9 |
| PLATELETS x(10 ⁹ /L) | 130-370 | 135-400 |
| NEUTS (x10 ⁹ /L) | 2.0-7.1 | 2.0-7.1 |
| LYMPHS (x10 ⁹ /L) | 1.1-3.6 | 1.1-3.6 |
| MONOs (x10 ⁹ /L) | 0.3-0.9 | 0.3-0.9 |
| EOSINS (x10 ⁹ /L) | 0.0-0.5 | 0.0-0.5 |
| BASOs (x10 ⁹ /L) | 0.0-0.2 | 0.0-0.2 |
| RETIC# | 20.0-92.0 | 12.0-96.0 |
| ESR ((mm/hr) | 1-10 | 1-20 |
 - Renal function:

| | | |
|------------------------------------|--------|--------|
| Creatinine (umol/L) | 60-125 | 55-110 |
| eGFR >59 mL/min/1.73m ² | | |

EXCLUSION CRITERIA

- Weight change of ≥ 3 kg in the preceding 2 months
- Undergone any weight loss surgery or gastric procedures to promote weight loss
- Current smokers
- Substance abuse
- Excess alcohol intake
- Pregnancy
- Diabetes
- Cardiovascular disease
- Cancer
- Gastrointestinal disease e.g. inflammatory bowel disease or irritable bowel syndrome
- Kidney disease
- Liver disease
- Pancreatitis
- Use of medications likely to interfere with energy metabolism, appetite regulation and hormonal balance, including: anti-inflammatory drugs or steroids, antibiotics, androgens, phenytoin, erythromycin or thyroid hormones.

Any participants with the above conditions would already have an altered pattern of hormones and inflammatory molecules because of their disease process and would therefore give us confounding or misleading results.

WITHDRAWAL CRITERIA

The safety of the study participants takes priority. Any significant adverse event (as assessed by the researchers) will halt the study and the ethics committee and sponsor will be informed as per standard protocol. All adverse events will be recorded and investigators will review each adverse event as it arises. In addition, participants will be free to withdraw at any time and are not required to give a reason.

STATISTICAL PLAN

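### Pregnancy is excluded and tested for, but breastfeeding and eating disorders are neither excluded nor asked about in a trial of sustained energy restriction with repeated buffet meals in excess

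*Combined protocol and SAP*

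**What the plan says.** **Eligibility.** The inclusion criteria ask for "Healthy overweight and obese volunteers" aged 18 to 65 with BMI 25 to 35 kg/m² and blood results within listed ranges. The word healthy is not defined further. The exclusion criteria name pregnancy, a set of physical diseases, substance abuse, excess alcohol, smoking and weight-loss procedures. They also exclude medications likely to disturb energy metabolism, appetite or hormones, and "Weight change of ≥ 3 kg in the preceding 2 months". The stated reason for the list is that "Any participants with the above conditions would already have an altered pattern of hormones and inflammatory molecules because of their disease process".

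**Screening (Visit 1).** "They will have a blood test (FBC, ALT, HbA1C, renal function, and lipids) and height and weight measurements will also be taken". An ECG and blood pressure follow, and "All women of childbearing age will have a pregnancy test". No other health question is described.

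**Diet (Visit 2).** Resting energy expenditure is measured by calorimetry. Then "The calories needed per day for each subject will be estimated and a -500 kcal/day diet will be provided" for the rest of the study. A 7-day food diary also informs the individual diet, and the booklet is built around the resting requirement.

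**Test meals.** "Food intake will be assessed at 240 min by offering a free buffet meal served in excess". This is done at the acclimatisation visit and, because those measurements are repeated, again at weeks 1 and 12.

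**Safety.** The Withdrawal Criteria section puts participant safety first.

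**The concern.** The trial restricts energy intake and measures weight, appetite, gut hormones and free intake. Breastfeeding bears on energy and hormonal balance, and an eating disorder bears on appetite and eating behaviour. The protocol already screens out drugs that act on these same systems, and it tells participants not to start other diets or intensive exercise because these could confuse the results. Leaving the two conditions out is inconsistent with that approach.

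The first thing at stake is the participant. A breastfeeding woman could be given a deficit that takes no account of milk energy. A person with a current eating disorder could be put through prolonged restriction combined with unlimited test meals. The effect on the trial's results is a lesser matter.

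**Working it through.** **1. Is either condition caught by a stated rule?** The two conditions set against each gate in the protocol:

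| Gate | Breastfeeding | Eating disorder |
|---|---|---|
| Pregnancy exclusion and test | No | No |
| Blood tests, ECG, blood pressure | Not designed to detect it | Not designed to detect it |
| BMI 25 to 35 | No | Stops only those outside the range |
| Weight change of 3 kg or more in 2 months | Stops some, not the weight-stable | Stops some, not the weight-stable |
| Medication exclusion | Only if taking a listed type | Only if taking a listed type |
| Healthy volunteer (undefined) | Not clearly | At the investigator's discretion, if known |

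No row closes the gap for a weight-stable volunteer. The age range includes women of childbearing age, so both groups can occur.

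**2. What would such a volunteer be exposed to?** A deficit of 500 kcal/day for about 12 weeks (84 days of supplement taken with the diet), and three buffets, at weeks 0, 1 and 12. The derivation of daily need is not given. If milk energy is not counted, the real deficit is 500 kcal/day plus the uncounted milk energy. If the food diary drives the estimate in a weight-stable woman, some milk energy is already included.

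**3. The plan's own sample size.** Difference 5.0 − 3.0 = 2.0 kg, SD 2.5 kg, alpha 0.05 (two-sided assumed), power 0.80. The t-test calculation gives 25.5, so 26 per group, with power 0.807. Allowing for drop-out, 26 / 0.75 = 34.7, so 35 per group and 70 in total. Both stated figures reproduce, and the proposed change does not alter them.

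**4. How far could one breastfeeding participant move the weight result?** The documents give no milk-energy figure. Assume 300 to 600 kcal/day, none of it allowed for in the diet, no compensating intake, and 7,700 kcal per kg.

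- Extra loss over 84 days: 300 × 84 / 7,700 = 3.3 kg; 600 × 84 / 7,700 = 6.5 kg.
- Shift in a 26-person arm mean: 3.27 / 26 = 0.13 kg; 6.55 / 26 = 0.25 kg.
- Share of the planned 2.0 kg: 6% to 13%.
- Standard error of the between-arm difference: 2.5 × √(2/26) = 0.69 kg. The shift is 0.18 to 0.36 of this.

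**5. Is that conversion too generous?** On the same conversion the planned deficit alone gives 500 × 84 / 7,700 = 5.5 kg, but the protocol expects 3.0 kg from diet alone, which is 55% of it. Scaling by 0.55 gives an extra loss of 1.8 to 3.6 kg and a shift of 0.07 to 0.14 kg, or 3.5% to 7% of 2.0 kg. Part of the shortfall may be non-adherence, so this is a sensitivity check and not a correction.

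**6. Eating disorder, appetite, hormones, buffet intake.** The documents contain nothing from which an effect could be computed.

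**The case against.** The strongest reply is that existing gates do part of the work. The 3 kg rule would stop some women after childbirth and some people with an active eating disorder. An investigator could use the healthy-volunteer requirement to turn away a known case, and weight and diet are reviewed at weeks 4 and 8. This stands in part. It narrows the group at risk, but it does not remove weight-stable volunteers, and nobody is told to ask. Consent pages are not in the file and may carry a question or warning, although that would not change the listed criteria.

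A second reply is that the stated reason for the exclusions refers to disease, and breastfeeding is not a disease. That is correct, but pregnancy is not one either, and it is listed.

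Three stronger readings are tempting, and the documents do not support them:

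- A reader might infer that a breastfeeding participant's deficit is certain to exceed 500 kcal/day because it is set from a resting measurement. The protocol does not say how daily need is derived, and it also uses a food diary. The excess is possible, not established.
- A reader might infer that one or two such participants would distort the results. For weight, the illustrative shift per participant is well below one standard error. Allocation is randomised, so such participants add noise and not systematic bias. For the other outcomes there is no estimate.
- A reader might infer that any history of an eating disorder should exclude. An open-ended rule of that kind is debatable, and nothing in the documents settles it.

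**Conclusion.** The gap is real: both conditions are absent from the criteria and from the screening described, and no other rule reliably catches them. The case for acting rests on participant safety and on consistency with the protocol's own exclusions. It does not rest on a statistical effect. Few such volunteers are expected, and any effect on the arm means is small and cannot be estimated from the documents. The range of 0.07 to 0.25 kg per breastfeeding participant depends entirely on the assumed milk energy, energy conversion and lack of compensation, and serves only to show scale. The claim of a larger deficit is conditional on the daily-need estimate making no allowance for milk energy.

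**What to change.** Add breastfeeding and current eating disorder to the exclusion criteria, each checked by a direct question at Visit 1 and recorded with the other screening results. The sponsor should decide, and state in the protocol, how a past eating disorder is handled.

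The cost is a minor amendment, two screening questions and possibly a few volunteers excluded. The sample size and the analysis need no change.

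### A normality check of unspecified data picks t-test or rank test while a mean difference is always reported, and the blood ANOVA has no stated scale or fallback; the main cost is power for right-skewed blood markers

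*Combined protocol and SAP*

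**What the plan says.** The Statistical Plan is one paragraph. It states "Data will be checked for normality using a Shapiro-Wilk test (defined as" P ≥ 0.01), so P at or above 0.01 is counted as normal. Means are then "compared within and between groups using a paired t-test or Wilcoxon signed-rank test where applicable". The text does not spell out that the first sentence governs the second, but the normality check has no other stated purpose, so that is the natural reading. No outcome, including weight, is given a fixed test. The plan does not say whether the check applies to each arm or to both pooled, or to levels, changes or residuals.

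Reporting does not depend on the test used: "The results express as mean difference with" its standard error.

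Blood outcomes have their own sentence: "Analysis of variance will assess the impact of two different interventions (IPE and Inulin) on participant blood parameters across the 12-week supplementation period", using baseline and week 12, with group as the between-subjects factor. The Visit 3 section lists the measurements: "These will include glucose, insulin, gastrointestinal and appetite hormones", and short-chain fatty acids. No log or other transformation appears anywhere, and no alternative is given if the blood data fail the check.

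**The concern.** There are two separate issues.

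**Coherence and pre-specification.** The test for each outcome is chosen after the data are seen, by a rule that leaves open what is checked. If the rule moves to ranks, the p-value no longer tests the mean difference that is printed beside it.

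**The scale of the blood markers.** Hormones, insulin and short-chain fatty acids may be right-skewed. If they enter the ANOVA untransformed, a few large values can dominate the variance and real differences become harder to detect. With about 26 evaluable participants per arm there is little power to spare.

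**Working it through.** **1. The plan's own sample size.** The section on number of volunteers expects losses of 3.0 and 5.0 kg, each with SD 2.5 kg, at p = 0.05 and power 0.80. The standardised difference is d = (5.0 − 3.0)/2.5 = 0.8. The normal approximation, two-sided, is n = 2(1.960 + 0.842)²/0.8² = 24.5, so 25 per arm. The exact two-sample t calculation gives 25.5, so 26, which matches "26 volunteers will be need per group"; power at 26 is 80.7%. For 25% dropout, 52/0.75 = 69.3, so 70. Both figures reproduce. The calculation is for a difference in means between independent arms.

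**2. The check applied to weight.** Assume weight change is roughly normal and each arm is checked separately. Each arm is flagged about 1% of the time, so either arm is flagged in 1 − 0.99² = 2.0% of trials. In simulation, switching test changes the verdict in 0.2% of trials.

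**3. The check applied to skewed data.** Simulation, 26 per arm, assumed lognormal:
- A single arm's levels are flagged in 6% of samples at log-SD 0.2, rising to 93% at log-SD 1.0.
- A single arm's change scores (correlation 0.7) are flagged in 5% at log-SD 0.3, 18% at 0.5 and 47% at 0.8.

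Next, the two-stage rule was run on levels: an independent t-test if both arms pass, otherwise Mann-Whitney. The true effect was 0.8 SD on the log scale. Independent-sample tests were used because the paired tests named in the plan cannot compare separate arms, which is a different fault.

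| Log-SD | Pre-set log t-test | Raw t-test | Two-stage rule |
|---|---|---|---|
| 0.3 | 82% | 81% | 82% |
| 0.5 | 81% | 77% | 80% |
| 0.7 | 81% | 72% | 80% |
| 1.0 | 82% | 63% | 80% |

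The two-stage rule's type I error was 4.8% to 5.5% (Monte Carlo error about 0.4 points). In this table the rule costs 0 to 2 points against the log-scale test. Across the other settings examined, including change scores, the cost is about 0 to 5 points in most.

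**4. The blood ANOVA.** With two visits and two groups, the group-by-visit test is equivalent to a two-sample t-test on change scores. Taking that as the effect of interest, let s be the log-SD at each visit and 0.7 the correlation of log values. The SD of the log change is s√(2(1 − 0.7)) = 0.775s. An effect of 0.8 of that SD is a shift of 0.62s; at s = 0.5 this is 0.31, a ratio of e^0.31 = 1.36. The coefficient of variation (CV) is √(exp(s²) − 1).

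| Log-SD | CV of levels | Raw-change power | Log-change power | Difference (points) |
|---|---|---|---|---|
| 0.3 | 0.31 | 81% | 81% | 0 |
| 0.5 | 0.53 | 77% | 81% | 4 |
| 0.8 | 0.95 | 67% | 80% | 13 |
| 1.0 | 1.31 | 58% | 82% | 24 |

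On the log scale the change is normal with d = 0.8 in every row, so the exact power is the 80.7% of step 1. The spread from 80% to 82% is simulation error.

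**The case against.** The strongest reply is that the normality check is close to harmless. Type I error holds, the power cost is small, and weight, the only outcome with a power calculation, is almost untouched if its change is roughly normal. For strongly skewed data the check even helps: at log-SD 1.0 the two-stage rule has 80% power, against 63% for a raw t-test used throughout. The documents report no distribution for any marker, so the need for a log scale is assumed. Silence about transformation is also not a statement that none will be used.

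All of this stands, and it limits the point. Two stronger readings should therefore be set aside. A reader might infer that the choice of test is essentially random for skewed outcomes. The documents do not support that: they give no skewness, the flag rate for levels runs from 6% to 93% over the range assumed, and any rate of disagreement between arms, or between levels and changes, needs a reading of *data* that the plan does not state. A reader might also infer inflated false positives; the simulation does not show this.

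What the reply leaves untouched is narrower. The reassurance on type I error applies to a rule fixed in advance, and this one leaves open what is checked. The mismatch between a rank p-value and a mean difference remains whenever the rule switches. The ANOVA has neither a stated scale nor an alternative.

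**Conclusion.** The point holds in limited form and is worth a cheap correction. The plan fixes no test per outcome, can pair a rank-based p-value with a mean difference, and leaves the scale of the blood analysis unstated. The normality check alone is a fault of pre-specification and coherence more than of error rates.

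The material cost is conditional. If the blood markers are analysed untransformed, the loss is nil at log-SD 0.3, about 4 points of power at 0.5, about 13 at 0.8 and about 24 at 1.0. These figures assume lognormal markers, an effect that is multiplicative, correlation 0.7 between visits, 26 per arm, and the group-by-visit effect as the target. For a nearly symmetric marker there is no loss to recover.

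**What to change.** Rewrite the Statistical Plan so that no normality test selects an analysis:

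- **Weight:** compare weight change between arms as a difference in means, by a Welch test or a baseline-adjusted linear model, whatever a normality test shows. This is the quantity on which the sample size was based.
- **Insulin, gut hormones and short-chain fatty acids:** analyse on a log scale fixed in advance, and report ratios with confidence intervals. State the scale for glucose too.
- **Rank tests:** keep them as labelled sensitivity analyses. Check residuals by plot.

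This changes wording only; it needs no further participants or measurements. The costs are that blood results are read as ratios, and that the plan must state how values below the assay limit are handled before logs are taken.
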